9.10 Assessments of reactogenicity

For all participants, baseline assessments are performed before and reactogenicity assessments are performed after each vaccination. All reactogenicity symptoms are followed until resolution and graded according to the Division of AIDS Table

for Grading the Severity of Adult and Pediatric Adverse Events, Corrected Version 2.1, July 2017, except as noted in Section 11.2.2.

The reactogenicity assessment period is 7 full days for Part A and Part B and 14 full days for Part C following each vaccination per the assessment schedule shown in Table 9-1. Participants are instructed to record symptoms using a Participant Diary. Contacts between the participant and the site staff should take place at least once between 1-3 days postvaccination. In general, a participant who self-reports any postvaccination reaction greater than mild is seen by a clinician within 48 hours after onset, unless the reaction is improving and/or has completely resolved. Clinic staff will follow new or unresolved reactogenicity symptoms present at day 7 (Parts A & B) or day 14 (Part C) to resolution.

Reactogenicity events are reported using CRFs that correspond to the time of assessment in Table 9-1. Reactogenicity assessments include assessments of systemic and local symptoms, and vaccine-related lesions. Events not listed on a CRF, or with an onset after the reactogenicity assessment period (day of vaccination and 7 full days after for Part A and Part B and 14 full days after for Part C), or those meeting SAE/adverse events requiring expedited reporting according to DAIDS criteria, are recorded on an adverse event log form.

Table 9-1 Schedule of reactogenicity assessments

Day	Time	Performed by
0 ^a	Baseline: before vaccination	HVTN CRS clinician
	Early: 25-60 minutes after vaccination	HVTN CRS clinician
	Between early assessment and 11:59pm day 0	HVTN CRS clinician or participant
1-7 ^b	Between 12:00am and 11:59pm on the respective day	HVTN CRS clinician or participant
1-14 ^c	Between 12:00am and 11:59pm on the respective day	HVTN CRS clinician or participant

^a Day of vaccination

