Second, this protocol will evaluate BG505 SOSIP.664 gp140 separately combined with four different adjuvant formulations that activate different innate immune pathways; a separate placebo group will receive Tris-buffered saline. Three adjuvants are newly developed in this decade (GLA-LSQ, 3M-052-AF, and CpG 1018) and the fourth is the licensed Alum adjuvant (Alhydrogel) as an active control. The study aims to identify at least one novel trimer-adjuvant formulation that induces more potent, durable neutralizing antibodies to the tier 2 BG505 subtype A viral strain than the trimer-Alum formulation. This study provides a unique opportunity to compare a single common antigen, the first-in-class stable Env SOSIP trimer, with four clinical-grade adjuvants available in humans. The indepth analyses of safety and immunological effects may lead to identification of a more suitable adjuvant than Alum for Env immunogens in future studies, as well as a platform for novel adjuvant discovery in first in human studies. For example, building on information obtained in Part A of this protocol, we will evaluate a stabilized Env SOSIP trimer (Trimer 4571) in combination with 3M-052-AF to see if neutralization activity in human sera can be improved by combining a

stabilized trimer with a promising adjuvant. Trimer 4571 has two amino acid differences with BG505 SOSIP.664, designed to mimic the vulnerable prefusion state. By fixing the trimeric protein into this configuration, in theory this should allow for more visibility to the immune system and greater degree of neutralization. This theory will be directly tested in Part C. In addition, Part C will also test whether an intermediate dose (3 mcg) of the 3M-052 AF plus Alum leads to equivalent neutralization to the high dose (5 mcg, evaluated in Parts A and B) when combined with the original BG505 SOSIP.664 and establish the tolerability of this dose The intended purpose of this arm is to test whether an intermediate dose of this promising adjuvant can drive similar immune responses and therefore will be important for clinical development of this adjuvant.

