The protocol team therefore desires to build on these exciting results with a goal of optimizing the 3M-052 AF + Alum for advancement of this product.

Using the same schedule, we propose to determine whether a 3-mcg dose of 3M-052 AF + Alum is sufficient to drive tier 2 autologous neutralization with less systemic reactogenicity than observed with the 5-mcg dose.

Additionally, we propose to test whether the VRC trimer 4571 adjuvanted with 3M-052 AF leads to the development of tier 2 (both autologous and heterologous) neutralizing antibodies. The VRC 4571 trimer is a stabilized BG505 trimer designed to better elicit nAbs. The VRC trimer 4571 was formulated in Alum in a recent VRC phase 1 trial, but no autologous nAbs were elicited. This trial used Alum as an adjuvant. To test whether there is a conceptual issue with trimer design or, alternatively, whether the adjuvant is a critical mediator for neutralization, we proposed to add an arm testing whether VRC 4571 leads to

neutralization of the autologous and other tier 2 viruses. This is a critical question for the field because it will determine whether the conceptual framework (that alterations in the stabilization of a trimer will lead to improved neutralization) is accurate.

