6.4.3.1 Reactogenicity

The number and percentage of participants experiencing each type of reactogenicity sign or symptom will be tabulated by severity and treatment arm and the percentages displayed graphically by arm. For a given sign or symptom, each participant's reactogenicity will be counted once under the maximum severity for all injection visits. In addition, to the individual types of events, the maximum severity of local pain or tenderness, induration or erythema, and of systemic symptoms will be calculated. Kruskal-Wallis tests will be used to test for differences in severity between arms.

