9.10.1 Assessment of systemic and local symptoms

Systemic symptoms include increased body temperature, malaise and/or fatigue, myalgia, headache, chills, arthralgia, and nausea. Local symptoms include pain and/or tenderness at the injection site. The daily maximum severity reached for each symptom during the assessment period is reported.

Body temperature is measured by oral or infrared thermometry. All temperatures must be measured by non-axillary thermometry. This includes temperatures taken in the clinic, as well as temperatures taken by participants during the reactogenicity period.

^b New or unresolved reactogenicity symptoms present on day 7 are followed until resolution for Parts A and B

^c New or unresolved reactogenicity symptoms present on day 14 are followed until resolution for Part C

Temperature is reported in degrees Celsius. If temperature is measured in Fahrenheit, the conversion to Celsius should be documented in the participant's chart note. A measurement is taken once daily during the assessment period and should be repeated if participant is feeling feverish.

Participants with evidence of moderate to severe reactogenicity may be asked to come to the clinic for additional assessment and/or blood sampling.

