⁵ Includes pretest steps and HIV testing. A subsequent follow-up contact is conducted to provide post-test steps and to report results to participant. If a participant has a confirmed diagnosis of HIV infection, do not perform HIV infection assessment.

⁶ As appropriate for participants providing rectal and/or vaginal mucosal samples (see Section 9.5).

⁷ For specimen collection requirements, see Appendix M, Appendix O, and Appendix P. For participants with a confirmed diagnosis of HIV infection, specimens for urinalysis and urine pregnancy tests listed under "Safety labs" in Appendix M, Appendix O, and Appendix P will be collected per the protocol schedule.

⁸ Not applicable to HIV-infected participants.

⁹ Blood draws required at vaccination visits must be performed prior to vaccination; however, it is not necessary to have results prior to vaccination, except for results of a urine or serum pregnancy test, if indicated. See Appendix M, Appendix O, and Appendix P.

¹⁰ Reactogenicity assessments performed daily for at least 7 days postvaccination for Part B. Reactogenicity assessments performed daily for at least 14 days postvaccination for Part C (see Section 9.10).

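### Reactogenicity is scored as a maximum over Days 0-14 in Part C but Days 0-7 in Parts A and B, so cross-part tolerability comparisons can only be shifted against the Part C arms

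*Protocol*

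**What the plan says.** Protocol Section 9.10 sets the window: "The reactogenicity assessment period is 7 full days for Part A and Part B and 14 full days for Part C following each vaccination". The day of vaccination counts as well, so the period is 8 calendar days per dose in Parts A and B and 15 in Part C. Appendix T repeats the split: "Reactogenicity assessments performed daily for at least 7 days postvaccination for Part B", and "Reactogenicity assessments performed daily for at least 14 days postvaccination for Part C". Section 9.10 sends an event that starts after the period to the adverse event log, and has symptoms present at the end of the period followed to resolution in every part.

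Section 9.10.1 fixes the recording level: "The daily maximum severity reached for each symptom during the assessment period is reported".

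Section 6.4.3.1 fixes the scoring: for a given sign or symptom, "each participant's reactogenicity will be counted once under the maximum severity for all injection visits". It adds that "Kruskal-Wallis tests will be used to test for differences in severity between arms". It states no window common to the three parts.

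Section 4.2.2, in the rationale for adding Part C, asks whether 3 mcg of 3M-052-AF + Alum is enough to drive neutralization "with less systemic reactogenicity than observed with the 5-mcg dose". Section 4.1 says where the comparison data lie: "the high dose (5 mcg, evaluated in Parts A and B) when combined with the original BG505 SOSIP.664". Those are Groups 2 and 4.

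**The concern.** The same headache starting on Day 10 is a reactogenicity event in Group 7 and an adverse event log entry in Group 4. In Group 7 it can raise the participant's score; in Group 4 it cannot. A maximum taken over more days is never smaller, so the mismatch works in one direction only. It makes the 3-mcg arm look more reactogenic than the same scoring window would, which is opposite to the hypothesis that Group 7 is meant to examine. Any comparison of Trimer 4571 (Group 8) with Group 4 is exposed in the same way. The adverse event tables shift the other way: late symptoms of the listed terms appear there for Parts A and B but not for Part C.

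With 10 vaccinees in a Part C arm, one participant moved up a category changes a percentage by 10 points. Even a modest artefact can therefore be visible in the table used to judge the dose.

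**Working it through.** **Inputs from the protocol.** Windows: Section 9.10. Scoring rule: Section 6.4.3.1. Three doses in Parts B and C, and two plus an optional third in Part A: Section 4.2.2. Vaccine arm sizes of 20 (Part B) and 10 (Part C): Sections 6.1.2 and 6.1.4. The clinical background reports that 9 of 17 Part A participants took the third dose.

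**The plan's nearest own figure.** Section 6.1.4 says that 10 vaccinees give a 90% chance of at least one event at a true rate of 20.6%. Check: 1 - (1 - 0.206)^10 = 0.900. It reproduces. It is a per-arm detection figure, does not involve the window, and is not in dispute.

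**Direction.** For any participant, the maximum over Days 0-14 is at least the maximum over Days 0-7. Relative to a common Days 0-7 window, a Part C score can only stay the same or rise.

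**Scored days per participant.**
- Groups 7 and 8: 3 × 15 = 45.
- Group 4, and Group 2 with the third dose: 3 × 8 = 24.
- Group 2 with two doses: 2 × 8 = 16.
- Extra days, Group 7 over Group 4: 45 - 24 = 21.

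**Size.** The protocol gives no background symptom rate, so the daily onset rate h and the share p already reacting in Days 0-7 are both assumed. The chance of at least one late onset is 1 - (1 - h)^21. Only participants without an early reaction can be added to the any-symptom count, so the inflation is (1 - p) × [1 - (1 - h)^21].

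| h per day (assumed) | Late onset in 21 days | Added points, p = 20% | p = 50% | p = 80% |
|---|---|---|---|---|
| 0.1% | 2.1% | 1.7 | 1.0 | 0.4 |
| 0.2% | 4.1% | 3.3 | 2.1 | 0.8 |
| 0.5% | 10.0% | 8.0 | 5.0 | 2.0 |
| 1% | 19.0% | 15.2 | 9.5 | 3.8 |

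Example: 1 - 0.99^21 = 0.190, and 0.190 × (1 - 0.5) = 9.5 points.

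**Effect on the test.** A simulation compared 10 with 20 participants who had the same true early severity, with 4,000 runs per setting. Assumed early severities (none, grade 1, 2, 3) were 50/30/15/5% and 20/40/30/10%; late events were grade 1, 2 or 3 in 70/25/5%. With no late events, Kruskal-Wallis rejected in 0.055 and 0.051 of runs. With h from 0.2% to 1%, it rejected in 0.046 to 0.072. The share with grade 2 or higher rose by about 1 to 5 points (0.7 to 4.8).

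**After the change.** With Days 0-7 in every part, Groups 7 and 4 are each scored on 24 days, and the difference due to the window is zero.

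**The case against.** Several objections have force.

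- **The 3-mcg versus 5-mcg tolerability contrast is not a listed objective or endpoint.** This stands. Part C primary objective 1 evaluates Trimer 4571 without naming a comparator, and secondary objective 1 concerns neutralization. Section 6.4.3.1 does not say that arms from different parts enter one Kruskal-Wallis test. A reader might infer that a formal safety endpoint is compromised; the documents support only a distorted descriptive comparison, given as a purpose in the rationale.
- **The analysis plan could set the window.** It could, because daily severities are recorded. But the protocol has already fixed the scoring rule, and a plan that follows Section 6.4.3.1 literally reproduces the mismatch.
- **Vaccine reactions peak early.** The protocol lists fatigue, myalgia and headache in the first few days as common, and reports that reactions so far generally resolved within 7 days. A mild late symptom does not raise the score of someone who already had a moderate early one. This limits the size but not the direction.
- **Late symptoms in Parts A and B are not lost.** Correct: they are logged or followed to resolution. The difference lies in what enters the score.
- **The comparison is sequential and non-randomized anyway.** True, and that cannot now be removed. The window mismatch can.

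Two stronger readings are tempting. One is that 45 against 24 scored days nearly doubles apparent reactogenicity; that would hold only if vaccination caused almost no early symptoms. The other is that a real advantage of 3 mcg would be masked or reversed. Neither is shown, since most vaccine-caused peaks should fall inside both windows.

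**Conclusion.** The point holds as a one-directional distortion of unknown and possibly small size. The direction follows from the scoring rule and needs no assumption. The size is not determined by the protocol: about 0.4 to 15 points on any-symptom percentages, for assumed background onset of 0.1% to 1% per day and assumed early reaction rates from 80% down to 20%. The simulated type I error stays close to its level without late events, so the concern is with the estimated percentages and much less with the test. The three-dose day count applies to Group 4. Group 2 participants with two doses have fewer scored visits still, which acts in the same direction and needs its own correction.

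**What to change.** Add to Section 6.4.3.1:

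- All cross-part reactogenicity summaries and tests (Groups 7 and 8 against Groups 2 and 4) use severities from Days 0-7 after each dose.
- Comparisons with Group 2 use the same number of doses on both sides: either the first two doses, or three-dose recipients only.
- Part C Days 8-14 are tabulated separately, beside adverse event log entries of the same terms on the same days in Parts A and B.

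The 14-day collection in Part C stays as it is, and the daily severities needed are already recorded. The cost is a short addition to the text and one extra table. The small downside is that late Part C reactions are shown apart from the main comparison.

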9.10.1 Assessment of systemic and local symptoms

Systemic symptoms include increased body temperature, malaise and/or fatigue, myalgia, headache, chills, arthralgia, and nausea. Local symptoms include pain and/or tenderness at the injection site. The daily maximum severity reached for each symptom during the assessment period is reported.

Body temperature is measured by oral or infrared thermometry. All temperatures must be measured by non-axillary thermometry. This includes temperatures taken in the clinic, as well as temperatures taken by participants during the reactogenicity period.

^b New or unresolved reactogenicity symptoms present on day 7 are followed until resolution for Parts A and B

^c New or unresolved reactogenicity symptoms present on day 14 are followed until resolution for Part C

Temperature is reported in degrees Celsius. If temperature is measured in Fahrenheit, the conversion to Celsius should be documented in the participant's chart note. A measurement is taken once daily during the assessment period and should be repeated if participant is feeling feverish.

Participants with evidence of moderate to severe reactogenicity may be asked to come to the clinic for additional assessment and/or blood sampling.

9.10.2 Assessment of injection site

Typical injection site reactions are erythema/redness and induration/swelling. The maximum diameter for all injection site reactions is recorded.

All injection site reactions are monitored until resolution. Reactions with diameters greater than 5 cm are followed daily; otherwise, the frequency of follow-up is based on clinician judgment. See HVTN 137 SSP for detail.

9.11 Visit windows and missed visits

Visit windows are included in Appendix W. The procedures for documenting missed visits and out of window visits are described in the HVTN 137 SSP. If the missed visit is one that required safety assessments or local safety labs, HVTN CRS staff should attempt to bring the participant in for an interim visit as soon as possible.

Procedures performed at an interim visit are usually toxicity/safety assessments (including local safety labs) and HIV testing. Except for HIV testing, these procedures are performed only if they were required at the missed visit or if clinically indicated. HIV testing may be performed as deemed appropriate by the study staff. Blood samples for immunogenicity assays are not typically collected at interim visits. Detail will be provided in the HVTN 137 SSP.

If a missed visit required vaccination, please refer to Section 7.4.2 and Section 7.4.3 for resolution.

9.12 Early termination visit

In the event of early participant termination, site staff should consider if the following assessments are appropriate: a final physical examination, clinical laboratory tests (including urine dipstick, CBC with differential, and chemistry panel), pregnancy testing (note: for persons who are confirmed pregnant, pregnancy testing is not required, unless clinically indicated), social impact assessment, and HIV test. For participants who have a confirmed diagnosis of HIV infection, see Section 9.14.

9.13 Pregnancy

If a participant becomes pregnant during the course of the study, no more injections of study product will be given. During pregnancy, no more STI testing, mucosal collections or additional optional collections will be conducted. Remaining visits and study procedures should be completed unless medically contraindicated or applicable regulations require termination from the study. During follow-up in persons who are confirmed pregnant, pregnancy testing is not required, unless clinically indicated. If the participant terminates from the study prior to the pregnancy outcome, the site should make every effort to keep in touch with the participant in order to ascertain the pregnancy outcome. Pregnancies and pregnancy outcomes will be reported as described in the HVTN 137 SSP section on Pregnancy Management and Reporting. If the participant is no longer pregnant, refer to Section 7.4.3.

If the participant is no longer pregnant (as defined by two consecutive negative tests) or breast-feeding and study product administration and mucosal and additional optional collections can be performed within an appropriate visit window, these may resume with unanimous consent of the HVTN 137 PSRT.

9.14 HIV infection during the study

If a participant becomes HIV-infected during the course of the study, no additional study product will be administered. Participants will be encouraged to continue scheduled study visits for up to 12 weeks following their last study product administration. Follow-up duration for participants diagnosed with HIV infection may be adjusted in consultation with the CRS investigator and the HVTN 137 PSRT (eg, to avoid interference with participant initiation of HIV treatment). At postinfection follow-up visits, only specimens required for protocol-specified safety laboratory tests, urinalysis, and pregnancy tests will be collected (note: for persons who are confirmed pregnant, pregnancy testing is not required, unless clinically indicated); in addition, some clinic procedures may be modified or discontinued (see Appendix Q, Appendix R, and Appendix T).

10 Laboratory

10.1 HVTN CRS laboratory procedures

The HVTN 137 Site Lab Instructions and SSP provide further guidelines for operational issues concerning the clinical and processing laboratories. These documents include guidelines for general specimen collection, special considerations for phlebotomy, specimen labeling, whole blood processing, HIV screening/diagnostic testing, and general screening and safety testing.

Tube types for blood collection are specified in Appendix J, Appendix K, Appendix L, Appendix M, Appendix N, Appendix O, and Appendix P. For tests performed locally, the local lab may assign appropriate tube types.

In specific situations, the blood collection tubes may be redirected to another laboratory or may require study-specific processing techniques. In these cases, laboratory special instructions will be posted on the protocol-specific section of the HVTN website.

Of note, all assays described below are performed as research assays to evaluate the ability of the vaccine to induce immune responses in the context of the participants' genetic background and are not approved for use in medical care. Results from these assays are not made available to participants or medical professionals to guide treatment decisions.

10.2 Total blood volume

Required blood volumes per visit are shown in Appendix J, Appendix K, Appendix L, Appendix M, Appendix N, Appendix O, and Appendix P. Not shown is any additional blood volume that would be required if a safety lab needs to be repeated, or if a serum pregnancy test needs to be performed. The additional blood volume would likely be minimal. The total blood volume drawn for each participant will not exceed 500 mL in any 56-day (8-week) period.

The preferred laboratory specimen tube types for research samples are shown in Appendix J, Appendix K, Appendix L, Appendix M, Appendix N, Appendix O, and Appendix P. Alternate tube types may be used under certain circumstances (eg, ACD tube shortages) upon approval of the HVTN Laboratory Center. Refer to the HVTN 137 Specimen Collection SSP for more information.

